8.5 Pregnancies

For subjects who become pregnant during the first 16 weeks on study, every attempt will be made to follow them to completion of pregnancy to document the outcome, including information regarding any complications with pregnancy and/or delivery. The pregnancy outcomes are captured by the pregnancy eCRF. Pregnant subjects are discontinued from receiving the study injections.

A table summarizing the total pregnancies, number of live births, and number of spontaneous abortions, elective abortions or stillbirths by treatment will be presented (Table 14.3.7, Appendix I). In addition, a listing of pregnancies and outcomes will be presented (Listing 16.2.11, Appendix III).

8.6 Clinical Laboratory Evaluations

Safety laboratory parameters evaluated from serum will include only the liver function test measuring ALT. Hematology parameters include hemoglobin, white blood cells (WBC), red blood cells (RBC), hematocrit, mean corpuscular volume (MCV), platelets, and absolute values for lymphocytes, neutrophils, eosinophils, monocytes and basophils. Sites enter the absolute values for the laboratory parameters and the system calculates percentage values. Laboratory safety evaluations are scheduled at week 4, 8, 16, 24, 32, 40, 48, 56, 64, and 72. Clinical laboratory results by subject will be presented in Listings 16.2.8.1 – 16.2.8.2, Appendix III.

As a note, the lab data for site PRCTRC were initially entered as percentage values but, in June 2016, the site switched to reporting absolute values with their respective units. This caused some discrepancy between calculated values in the database and data collection forms at the site. This could influence precision and will be considered as lab data are reported.

Only results for scheduled routine visits will be included in these analyses. In particular, laboratory results obtained at visits other than Week 4 and 8 for diagnosis of AEs will not be included.

Safety laboratory evaluations will be graded as follows: mild (grade 1), moderate (grade 2), severe (grade 3), or life-threatening (grade 4).

Safety laboratory results will be tabulated for each measure by study visit, treatment group, age stratum and grade (**Table 14.3.4.1, Appendix I**). The mean change from baseline along with 95% CI at each time point measured in the study will be computed (**Table 14.3.4.2, Appendix I**). Boxplots of safety laboratory values will be generated for baseline values and for values measured during the course of the study. Each boxplot will show the 1st quartile, the median, and the 3rd quartile, with values smaller than the 1st quartile or larger than the 3rd quartiles plotted as outliers. If appropriate, horizontal lines representing boundaries for abnormal values will be plotted.

Post dose 1 measures may also be summarized using shift tables to compare baseline and follow-up values (**Tables 14.3.4.4.x – 14.3.4.5.x, Appendix I**). Shift tables may be analyzed using Generalized Estimating Equations to account for the longitudinal nature of these data, as follows:

1) For laboratory parameters with two categories: Normal and abnormal (Binary response)

- a. For each parameter, the shift table displays the number of subjects who are categorized as normal or abnormal at baseline cross tabulated with normal or abnormal results at the post-vaccination visit.
- b. A GEE for the binary responses above is fitted and used for parameter estimation
 - Observation (y_{ij}, X_{ij}) for each subject $i = 1, \dots, n$ and repeated measurement time point $j = 1, \dots, J$
 - dependent variable $y_{ij} = \begin{cases} 1 & \text{abnormal} \\ 0 & \text{normal} \end{cases}$, independent variable $X_{ij} = (group_{ij}, time_{ij}, group_{ij} * time_{ij})$;
 - probability of abnormal is $p_{ij} = \Pr(y_{ij} = 1)$;
 - model: $g(p_{ij}) = X'_{ij}\beta$ using the logit link;
 - GEE: $\sum_{i=1}^n \left(\frac{\partial P_i}{\partial \beta}\right) V_i^{-1}(\alpha)(Y_i - P_i) = 0$ where $V_i(\alpha)$ is the working covariance matrix;
 - Implementation: PROC GENMOD (SAS) using SUBJECT option in the REPEATED statement to identify the cluster variable
 - Output: point estimates and 95% CI for the individual levels of the GROUP, TIME and GROUP*TIME variables, and Type-3 SAS output for the parameter significance;
 - Other analysis and outputs: Odds ratio with associated 95% CI of observing abnormality (from the fitted logistic model). Implemented with LSMEANS statement in PROC GENMOD.

2) For laboratory parameters with four categories: Grade 1, Grade 2, Grade 3, and Grade 4 (Ordinal response)

- a. For each parameter the shift table displays the number of subjects who are categorized as grade 1, grade 2, grade 3, or grade 4 at baseline cross tabulated with grade 1, grade 2, grade 3, or grade 4 results at the post-vaccination visit.

- b. A GEE model for the ordinal responses above are fitted and used for parameter estimation
- Observation (Y_{ij}, X_{ij}) for each subject $i = 1, \dots, n$ at time point $j = 1, \dots, J$. $Y_{ij} = (y_{ij1}, y_{ij2})$ is the ordinal response variable with 3 ordered categories;
 - Cumulative probability $p_{ijk} = \Pr(y_{ijk} = 1: \text{in lower } k \text{ category}) = \Pr(Y_{ij} \leq k), k = 1, 2$;
 - Proportional Odds model $\begin{cases} g(p_{ij1}) = \mu_1 + X'_{ij}\beta \\ g(p_{ij2}) = \mu_2 + X'_{ij}\beta \end{cases}$ using the logit link;
 - $X'_{ij}\beta = \sim \beta_1 t_{ij} + \beta_2 \text{group}_{ij} + \beta_3 t_{ij} * \text{group}_{ij}$
 - GEE: $\sum_{i=1}^n \left(\frac{\partial P_i}{\partial \beta} \right) V_i^{-1}(\alpha) (Y_i - P_i) = 0$ where $P_i = E(Y_i)$ $V_i(\alpha)$ is the working covariance matrix;
 - Output: estimated of two intercepts from the two fitted logistic models; point estimates and 95% CI for the individual levels of the GROUP, TIME and GROUP*TIME variables, and Type-3 SAS output for the parameter significance (chi-Square test);

The study is not powered to detect differences by vaccine group, therefore the absence of statistically significantly differences should not be interpreted that no such differences exist.

Individual clinical laboratory results for hematology and chemistry will be presented in **Listing 16.2.8.1 – 16.2.8.2, Appendix III**. Laboratory summary statistics are presented in **Table 14.3.4.2, Appendix I**. Box plots for laboratory results are presented in **Figures 14.5.1 – 14.5.x, Appendix II**. A listing of abnormal laboratory results is presented in **Table 14.3.4.3, Appendix I**.

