8.5. Risks and Benefits

8.5.1. Risks of Blood Collections:

The blood collection procedures are common in routine medical practice. The risks of blood sample collection are minimal and consist of mild discomfort at the sample collection site. The procedure may cause mild pain, bruising, fainting, and, rarely, infection at the site where the blood is taken.

8.5.2. Risks of the CHIKV VLP Vaccine:

In VRC 311, the first human trial in which the CHIKV VLP vaccine was administered to 25 subjects, the local and systemic reactogenicity was no more than mild and none of the subjects reported fever. It is possible that once administered to a larger number of subjects, other potential side effects from injection may be observed similar to those seen with other vaccines. Although not previously observed with the CHIKV VLP vaccine, this includes the possibility of anaphylaxis. With vaccines in general, local reactogenicity may include pain, tenderness, redness or induration of the skin at the injection site and systemic reactogenicity may include fever, chills, muscle aches, joint aches, nausea, headache, and fatigue. These side effects will be monitored, are expected to be short term and may or may not require treatment.

In VRC 311, seven laboratory test AEs (occurring in four participants) were assessed as related to study vaccine based on temporal relationship to vaccination. The AEs included four mild transient alanine aminotransferase increases and two mild and one moderate transient neutropenia. All resolved without clinical sequelae. There was no placebo comparison group in the VRC 311 study. The comparison of AEs in placebo and vaccine recipients in the VRC 704 study should provide a more detailed safety profile for the study vaccine.

8.5.3. Other Risks:

There should be no unusual risks associated with the CHIKV VLP vaccine. The effect of this vaccine on an unborn fetus is unknown. Female subjects of child bearing potential who are heterosexually active will be required to agree to use birth control beginning 21 days prior to enrollment and continuing through 12 weeks after last study injection. Women who are pregnant will be excluded from the study. Children will not be enrolled in this study.

8.5.4. Benefits:

Study participants may have no direct benefit from participation in this study but society may benefit from knowledge gained from research on the donated specimens. This protocol is not designed to provide treatment for any condition.

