Bilirubin – when accompanied by any increase in Liver Function Test increase by factor	1.1 – 1.25 x ULN	1.26 – 1.5 x ULN	1.51 – 1.75 x ULN	> 1.75 x ULN
Bilirubin – when Liver Function Test is normal; increase by factor	1.1 – 1.5 x ULN	1.6 – 2.0 x ULN	2.0 – 3.0 x ULN	> 3.0 x ULN
Cholesterol	201 – 210	211 – 225	> 226	---
Pancreatic enzymes – amylase, lipase	1.1 – 1.5 x ULN	1.6 – 2.0 x ULN	2.1 – 5.0 x ULN	> 5.0 x ULN

* The laboratory values provided in the tables serve as guidelines and are dependent upon institutional normal parameters. Institutional normal reference ranges should be provided to demonstrate that they are appropriate.

** The clinical signs or symptoms associated with laboratory abnormalities might result in characterization of the laboratory abnormalities as Potentially Life Threatening (Grade 4). For example, a low sodium value that falls within a grade 3 parameter (125-129 mEq/L) should be recorded as a grade 4 hyponatremia event if the subject had a new seizure associated with the low sodium value.

***ULN” is the upper limit of the normal range.

Hematology*	Mild (Grade 1)	Moderate (Grade 2)	Severe (Grade 3)	Potentially Life Threatening (Grade 4)
Hemoglobin (Female) - gm/dL	11.0 – 12.0	9.5 – 10.9	8.0 – 9.4	< 8.0
Hemoglobin (Female) decrease from baseline value - gm/dL	not applicable	1.6 – 2.0	2.1 – 5.0	> 5.0
Hemoglobin (Male) - gm/dL	12.5 – 13.5	10.5 – 12.4	8.5 – 10.4	< 8.5
Hemoglobin (Male) decrease from baseline value – gm/dL	not applicable	1.6 – 2.0	2.1 – 5.0	> 5.0
WBC Increase - cell/mm ³	10,800 – 15,000	15,001 – 20,000	20,001 – 25,000	> 25,000
WBC Decrease - cell/mm ³	2,500 – 3,500	1,500 – 2,499	1,000 – 1,499	< 1,000
Lymphocytes Decrease - cell/mm ³	750 – 1,000	500 – 749	250 – 499	< 250
Neutrophils Decrease - cell/mm ³	1,500 – 2,000	1,000 – 1,499	500 – 999	< 500
Eosinophils - cell/mm ³	650 – 1500	1501 - 5000	> 5000	Hypereosinophilic
Platelets Decreased - cell/mm ³	125,000 – 140,000	100,000 – 124,000	25,000 – 99,000	< 25,000
PT – increase by factor (prothrombin time)	1.10 x ULN**	1.11 – 1.20 x ULN	1.21 – 1.25 x ULN	> 1.25 ULN
PTT – increase by factor (partial thromboplastin time)	1.10 – 1.20 x ULN	1.21 – 1.4 x ULN	1.41 – 1.5 x ULN	> 1.5 x ULN
Fibrinogen increase - mg/dL	400 – 500	501 – 600	> 600	--
Fibrinogen decrease - mg/dL	150 – 200	125 – 149	100 – 124	< 100 or associated with gross bleeding or disseminated intravascular coagulation (DIC)

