Total	[column total]		[sum of 4 blocks, should be N]			
<<Post Dose One Visit 2>>						
Normal						
Abnormal						
Total						
Continue for all Post Dose One visits						

1. Footnote defines when pre-dose measurement was taken

TABLE 14.3.4.5.x:

Shift Table for <<ordinal-graded laboratory parameter>> by Treatment Group Comparing Pre-Dose One Measure to Post-Dose One Measures <<Overall/Site>>

	CHIKV (N=X) Baseline					Placebo (N=X) Baseline				
Pre-Dose One ¹	Grade 1	Grade 2	Grade 3	Grade 4	Total	Grade 1	Grade 2	Grade 3	Grade 4	Total
Grade 1	x	x	x	x	x	x	x	x	x	x
Grade 2										
Grade 3										
Grade 4										
Total										
Continue for all Post Dose One visits										

1. Footnote defines when pre-dose measurement was taken

TABLE 14.3.5:
Distribution of Vital Signs by Day Post Dosing, Grade, and Treatment Group <<Age Stratum, Overall/Site>>

[Implementation Note: If an assessment has a grading scale that includes grading for both high and low, then include one row for each severity for high and low.]

If data is not collected, enter 'N/A' for entry. (For example, Temperature at Post-Injection)

Repeat this table for Placebo group

Vital Signs Assessment	Severity	Pre-injection (Baseline) CHIKV (N=X)		Post-injection CHIKV (N=X)		Week 4 CHIKV (N=X)		Week 8 CHIKV (N=X)		Week 16 CHIKV (N=X)		Week 24 CHIKV (N=X)		Week 32 CHIKV (N=X)		Week 40 CHIKV (N=X)		Week 48 CHIKV (N=X)		Week 56 CHIKV (N=X)		Week 64 CHIKV (N=X)		Week 72 CHIKV (N=X)		Max Severity Post Baseline CHIKV (N=X)	
		n	%	n	%	n	%	n	%	n	%	n	%	n	%	n	%	n	%	n	%	n	%	n	%	n	%
Any Assessment	Normal	x	x.x	x	x.x	x	x.x	x	x.x	x	x.x	x	x.x	x	x.x	x	x.x	x	x.x	x	x.x	x	x.x	x	x.x	x	x.x
	Mild																										
	Moderate																										
	Severe																										
	Potentially Life Threatening																										
Systolic BP	Normal																										
	Mild																										
	Moderate																										
	Severe																										
	Potentially Life Threatening																										

Vital Signs Assessment	Severity	Pre-injection	Post-injection	Week 4	Week 8	Week 16	Week 24	Week 32	Week 40	Week 48	Week 56	Week 64	Week 72	Max Severity Post Baseline
		(Baseline) CHIKV (N=X)	CHIKV (N=X)	CHIKV (N=X)	CHIKV (N=X)	CHIKV (N=X)	CHIKV (N=X)	CHIKV (N=X)	CHIKV (N=X)	CHIKV (N=X)	CHIKV (N=X)	CHIKV (N=X)	CHIKV (N=X)	CHIKV (N=X)
Diastolic BP	Normal													
	Mild													
	Moderate													
	Severe													
	Potentially Life Threatening													

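### The laboratory grade table, shift tables and GEE ignore direction, so high and low values are pooled for white cells and for anything coded normal/abnormal

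*Combined protocol and SAP*

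**What the plan says.** SAP section 8.6 requires that "Safety laboratory results will be tabulated for each measure by study visit, treatment group, age stratum and grade". The shell, Table 14.3.4.1, gives every parameter the same rows: Normal, Outside Normal Range and Grade 1 to 4. It adds an *Any parameter* block and a maximum post-baseline severity column. No row carries a direction.

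The same section allows shift tables and GEE models of two kinds.
- The first is headed "For laboratory parameters with two categories: Normal and abnormal (Binary response"). Here "the shift table displays the number of subjects who are categorized as normal or abnormal at baseline", cross-tabulated with the post-vaccination result. The outcome is 1 for abnormal and 0 for normal, and the output includes "Odds ratio with associated 95% CI of observing abnormality (from the fitted logistic model").
- The second is headed "For laboratory parameters with four categories: Grade 1, Grade 2, Grade 3, and Grade 4 (Ordinal response").

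Neither item lists its parameters or mentions high and low.

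Protocol Appendix IV has one scale for WBC increase and another headed "WBC Decrease - cell/mm", each with four grades. It also says that hemoglobin above the upper limit of normal can be an adverse event, graded by the clinical criteria for systemic illness.

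For vital signs the SAP does handle direction. The note to Table 14.3.5 says that if an assessment is graded both ways, "then include one row for each severity for high and low". The laboratory shells have no such note.

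**The concern.** Laboratory measures through 4 weeks after the last injection are listed among the primary endpoints (SAP 3.2.1). A safety table should show which way values move. With the shells as written, a Grade 1 high white count and a Grade 1 low white count are the same entry, and maximum severity pools them again across visits. In the binary model, a subject who is high at baseline and low after dose 1 goes from abnormal to abnormal, which is no shift.

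If the vaccine lowers a count, high values from unrelated causes in both arms add to numerator and background alike. The risk difference survives, but the odds ratio, which is what the GEE reports, moves toward 1 and the comparison loses precision. The protocol (8.5.2) looks to this trial's placebo comparison for a more detailed safety profile than Phase 1 could give.

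**Working it through.** **1. Where direction is lost.** This compares the Appendix IV scales with the parameters in SAP 8.6 and Table 14.3.4.1.

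| Parameter | Appendix IV scale | Grade rows | *Outside Normal Range* row or normal/abnormal coding |
|---|---|---|---|
| WBC | increase and decrease | pooled | pooled |
| Hemoglobin | decrease; increases by clinical criteria | can be pooled | pooled |
| Neutrophils, lymphocytes, platelets | decrease only | one direction | pooled |
| ALT | increase only | one direction | pooled |
| RBC, hematocrit, MCV, monocytes, basophils | none | no grades defined | pooled |

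The last row holds the natural candidates for the binary item. WBC, neutrophils and ALT have four grades, so on the SAP's wording they belong to the ordinal item. That item's shift table (14.3.4.5.x) has no Normal category, so a change from normal to abnormal could be shown only in the binary table. The SAP does not say whether graded parameters will also be put there.

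**2. The plan's nearest figure.** No power is stated for laboratory comparisons. SAP Table 3 gives detectable event rates at 180 per group (200 × 0.9), two-sided 5%. For 1.0% against 7.5% at 80% power:
- Uncorrected n0 = [1.96 √(2 × 0.0425 × 0.9575) + 0.8416 √(0.01 × 0.99 + 0.075 × 0.925)]² / 0.065² = 150.0.
- With continuity correction, n = (n0/4)[1 + √(1 + 4/(n0 × 0.065))]² = 179.5, so 180.

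All eight pairs in that table give 179 to 181 by this formula. Exact Fisher power for this pair at 180 per arm is 85.4%, so the table is conservative at low rates.

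**3. Effect of pooling.** Let p0 and p1 be the proportions with a low value on placebo and vaccine, and h the proportion in each arm with an unrelated high value. High and low are taken as exclusive at a visit. Pooled rates are p0 + h and p1 + h. The risk difference stays p1 − p0. The odds ratio becomes [(p1 + h)/(1 − p1 − h)] / [(p0 + h)/(1 − p0 − h)]. For 2% against 8% with h = 5%, that is (0.13/0.87)/(0.07/0.93) = 1.99, against (0.08/0.92)/(0.02/0.98) = 4.26 with h = 0.

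Odds ratio and exact Fisher power, 180 per arm, two-sided 5%:

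| Low values, placebo v vaccine | h = 0 | h = 5% | h = 10% |
|---|---|---|---|
| 2% v 8% (assumed) | 4.3; 69% | 2.0; 41% | 1.6; 30% |
| 3% v 10% (assumed) | 3.6; 73% | 2.0; 48% | 1.7; 38% |
| 1.0% v 7.5% (pair from SAP Table 3) | 8.0; 85% | 2.2; 50% | 1.7; 36% |

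With h = 1%, the last pair gives odds ratio 4.6 and power 75%. The documents give no value for h.

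**The case against.** A reader might infer that this coding hides the Phase 1 signal. The documents do not support that. Phase 1 reported mild ALT increases and "two mild and one moderate transient neutropenia" (protocol 8.5.2). ALT is graded upward only and neutrophils downward only, each with its own rows in Table 14.3.4.1, so h = 0 in those grade rows. Dilution reaches these two signals only in the *Outside Normal Range* and *Any parameter* rows, or if they are also coded normal/abnormal. No Phase 1 signal in total white count is reported.

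Nor is direction lost from the laboratory analysis as a whole. Signed mean change with 95% CI (Table 14.3.4.2), boxplots and the listings keep it. Abnormal laboratory findings are adverse events (protocol 5.1.1), and SAP 8.3.2 compares unsolicited events between arms by preferred term with Fisher's exact test. Neutropenia and a raised white count would be different terms there.

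Three further points stand.
- Table 14.3.4.1 carries no test and the GEE is a repeated-measures logit model, so the power figures illustrate the dilution and do not describe a planned analysis.
- The SAP says that the study is not powered for laboratory differences and makes shift tables and GEE optional, although protocol 6.4.2 says they will be done.
- Eligibility limits baseline WBC, hemoglobin, platelets and ALT, so high-to-low changes in those should be few.

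None of this removes the pooling. Table 14.3.4.1 is not optional, and the GEE is the only between-arm model specified for the laboratory values themselves. The odds ratio is attenuated whatever the sample size.

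**Conclusion.** The concern holds in a limited form. Followed as written, the grade table, shift tables and GEE mix opposite events for WBC, possibly for hemoglobin, in the *Outside Normal Range* and *Any parameter* rows, and for every parameter coded normal/abnormal. For these, an odds ratio for abnormality does not estimate the risk of a low value or of a high one. In the illustration, a 5% rate of unrelated high values halves the odds ratio from 4.3 to 2.0 and cuts power from 69% to 41%. This rests on assumed rates, an equal high-value rate in both arms, and a Fisher test standing in for the GEE. The defect weakens some displays of a primary safety endpoint. It does not leave the trial unable to see neutropenia or a rise in ALT.

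**What to change.** Change SAP 8.6 and the laboratory shells as follows.
- **Table 14.3.4.1:** carry over the Table 14.3.5 note. Give separate high and low rows wherever both directions exist, including *Outside Normal Range* and *Any parameter*, and take maximum post-baseline severity within direction.
- **Normal/abnormal shift tables (14.3.4.4.x):** use Low, Normal and High.
- **Graded shift tables (14.3.4.5.x):** where a parameter is graded both ways, show increase and decrease grades separately.
- **GEE:** fit low against not low and high against not high as separate outcomes.
- **Parameter list:** state which parameters are treated as binary and which as ordinal.

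The cost is longer tables and a few more models. The values are already collected, and no grading scale or clinical rule changes.

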6.4.2. Safety Analysis

Reactogenicity: The number and percentage of subjects experiencing each type of reactogenicity sign or symptom will be tabulated by severity. For a given sign or symptom, each subject's reactogenicity will be counted once under the maximum severity for all assessments.

Adverse Events: AEs will be coded into Medical Dictionary for Regulatory Activities (MedDRA) preferred terms. The number and percentage of subjects experiencing each specific AE will be tabulated by severity and relationship to treatment. For the calculations in these tables, each subject's AE will be counted once under the maximum severity or strongest recorded causal relationship to treatment.

A complete listing of AEs for each subject will provide details including severity, relationship to treatment, onset, duration and outcome.

Safety Laboratory Values: Safety laboratory values will be summarized using shift tables to compare baseline and follow-up values. Shift tables will be analyzed using Generalize Estimating Equations to account for the longitudinal nature of these data. The mean change from baseline along with 95% confidence interval at each time point measured in the study will be computed. Boxplots of safety laboratory values will be generated for baseline values and for values measured during the course of the study. Each boxplot will show the 1st quartile, the median, and the 3rd quartile, with values smaller than the 1st quartile or larger than the 3rd quartiles plotted as outliers. If appropriate, horizontal lines representing boundaries for abnormal values will be plotted.

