- **Not Related** – There is not a reasonable possibility that the AE is related to the study agent.

Grading the Severity of Adverse Events:

The FDA Guidance for Industry (September 2007): “Toxicity Grading Scale for Healthy Adult and Adolescent Volunteers Enrolled in Preventive Vaccine Clinical Trials” is the basis for the severity grading of AEs in this protocol. Several modifications were made to the table as follows:

- “Emergency room visit” is not automatically considered a life-threatening event; these words have been removed from any “grade 4” definition where they appear in the table copied from the guidance document.
- Any laboratory value shown as a “graded” value in the table that is within the institutional normal range will not be severity graded or recorded as an AE.
- Severity grading for hemoglobin decrease on the basis of the magnitude of decrease from baseline is not applicable at the grade 1 level; only absolute hemoglobin will be used to define grade 1 decrease. Increases in hemoglobin are AEs only for values above the upper limit of normal and are graded by the systemic illness clinical criteria.
- Severity grading definition for Grade 4 local reaction to injectable product (Erythema/Redness and Induration/Swelling) included added text “requiring medical attention”.
- 1 X ULN was removed from the definition for PT increase.

When not otherwise specified in the table, the following guidance will be used to assign a severity grade:

Grade 1 (Mild): No effect on activities of daily living

Grade 2 (Moderate): Some interference with activity not requiring medical intervention

Grade 3 (Severe): Prevents daily activity and requires medical intervention

Grade 4 (Life-threatening): Hospitalization; immediate medical intervention or therapy required to prevent death.

Grade 5 (Death): Death is assigned a Grade 5 severity.

Only the single AE that is assessed as the primary cause of death should be assigned “grade 5” severity.

**Toxicity Grading Scale for Healthy Adult and Adolescent Volunteers Enrolled in
Preventive Vaccine Clinical Trials
FDA Guidance - September 2007**

A. Tables for Clinical Abnormalities

Local Reaction to Injectable Product	Mild (Grade 1)	Moderate (Grade 2)	Severe (Grade 3)	Potentially Life Threatening (Grade 4)
Pain	Does not interfere with activity	Repeated use of non-narcotic pain reliever > 24 hours or interferes with activity	Any use of narcotic pain reliever or prevents daily activity	Hospitalization

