Any SOC	Any PT					

Note: This table presents number of events.

**TABLE 14.3.2.1:
 Listing of Deaths and Serious Adverse Events**

[Implementation note: If event is ongoing at end of study, indicate as “Ongoing” in the “Duration” column.

If there are no comments for an event, populated “Comments” row with “None.”]

Part 1

Subject ID	Age (Years)	Treatment Group	AE Number	Adverse Event	Adverse Event Onset Date	Associated with Dose #	# of Days Post Associated Dose	Adverse Event End Date	Duration (Days)	Reason Reported as an SAE	Severity

Part 2

Subject ID	Adverse Event	Relationship to Study Treatment	Effect on Injection Schedule	Subject Discontinued Due to AE	Outcome	Comments

TABLE 14.3.2.2:
Listing of Non-Serious, Unsolicited, Moderate or Severe Adverse Events

[Implementation note: If there are no comments for an event, populated “Comments” row with “None.”]

Part 1

Subject ID	Age (Years)	Treatment Group	AE Number	Adverse Event	Adverse Event Onset Date	Associated with Dose #	# of Days Post Associated Dose	Adverse Event End Date	Duration (Days)	Severity	Relationship to Study Treatment

Part 2

Subject ID	Adverse Event	Effect on Injection Schedule	Subject Discontinued Due to AE	Outcome	Comments

TABLE 14.3.2.3:
Listing of New Onset Chronic Medical Conditions

[Implementation note: These conditions are met when AD12SAEA = '3' (Persistent/significant disability/incapacity) and/or AD12OTCM = '3' (Ongoing/persistent condition)]

Part 1

Subject ID	Age (Years)	Treatment Group	AE Number	Adverse Event	Adverse Event Onset Date	Associated with Dose #	# of Days Post Associated Dose	Adverse Event End Date	Duration (Days)	Severity	Relationship to Study Treatment

Part 2

Subject ID	Adverse Event	Effect on Injection Schedule	Subject Discontinued Due to AE	Outcome	Comments

TABLE 14.3.4.1:
Distribution of Laboratory Results by Parameter, Severity, Study Day, and Treatment Group <<Age Stratum, Overall/Site>>

[Implementation: Repeat this table for the Placebo group]

Lab. Param	Severity	Baseline CHIKV (N=X)		Week 4 CHIKV (N=X)		Week 8 CHIKV (N=X)		Week 16 CHIKV (N=X)		Week 24 CHIKV (N=X)		Week 32 CHIKV (N=X)		Week 40 CHIKV (N=X)		Week 48 CHIKV (N=X)		Week 56 CHIKV (N=X)		Week 64 CHIKV (N=X)		Week 72 CHIKV (N=X)		Max Severity Post Baseline CHIKV (N=X)			
		n	%	n	%	n	%	n	%	n	%	n	%	n	%	n	%	n	%	n	%	n	%	n	%		
		Any parameter	Normal	x	x.x	x	x.x	x	x.x	x	x.x	x	x.x	x	x.x	x	x.x	x	x.x	x	x.x	x	x.x	x	x.x	x	x.x
	Outside Normal Range																										

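### The ordinal shift table and GEE for laboratory grades have no Normal/ungraded level, and the model's three categories do not match the four grades declared

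*Combined protocol and SAP*

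**What the plan says.** SAP 8.6 divides the shift-table analysis in two. Item 1 covers parameters with two categories, normal and abnormal. Item 2 covers parameters with four categories, Grades 1 to 4. For the second kind, item 2a cross-tabulates "grade 1, grade 2, grade 3, or grade 4 at baseline cross tabulated with grade 1, grade 2, grade 3, or grade 4" results after vaccination. The shell of Table 14.3.4.5.x, titled "Shift Table for <<ordinal-graded laboratory parameter>> by Treatment Group Comparing Pre-Dose One Measure to Post-Dose One Measures", has Grades 1 to 4 plus a total on each margin and nothing else.

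Item 2b fits a proportional-odds GEE to those responses. It says the outcome "is the ordinal response variable with 3 ordered categories", writes cumulative probabilities for k = 1 and 2 only, and lists as output the "estimated of two intercepts from the two fitted logistic models".

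Protocol Appendix IV says that a laboratory value "that is within the institutional normal range will not be severity graded or recorded as an AE". SAP 8.6 defines Grades 1 to 4 and no grade 0.

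The two documents differ on whether the analysis will be done. Protocol 6.4.2 says "Shift tables will be analyzed using Generalize Estimating Equations to account for the longitudinal nature of these data". SAP 8.6 makes it optional: "Post dose 1 measures may also be summarized using shift tables to compare baseline and follow-up values", with the GEE likewise worded as something that may be done.

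**The concern.** In screened healthy adults, the shift that matters most is from a normal baseline to a graded result after injection. The ordinal table has no row or column for it. An ungraded visit also has no response value in the ordinal GEE, so the model can ask only whether graded results are more severe in one arm than in the other. A vaccine that produced more abnormalities of the same severity would leave no signal.

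The category mismatch is a second fault. Correcting the count alone would not bring Normal in, and adding Normal alone would not make the model match. A programmer could not implement item 2b without inventing a rule.

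Safety is the primary objective. ALT and neutrophils, both among the affected parameters, gave rise to all seven related laboratory AEs in the Phase 1 study (protocol 8.5.2).

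**Working it through.** **Category count.** A cumulative-logit model with K ordered categories has K − 1 intercepts.

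| Outcome | K | Intercepts | Shift-table cells |
|---|---|---|---|
| Grades 1–4, as declared in item 2 | 4 | 3 | 16 |
| Model in item 2b | 3 | 2 | 9 |
| Normal/ungraded plus Grades 1–4 | 5 | 4 | 25 |

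The SAP's two intercepts agree with its three categories, but not with the four grades above them. No version that keeps all four grades separate, with or without Normal, gives two.

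**Parameters affected.** SAP 8.6 lists 12: ALT, hemoglobin, WBC, RBC, hematocrit, MCV, platelets, lymphocytes, neutrophils, eosinophils, monocytes and basophils. Appendix IV gives four grades for seven: ALT, hemoglobin, WBC, platelets, lymphocytes, neutrophils and eosinophils. The SAP does not itself assign parameters to item 1 or item 2, so this allocation is read from Appendix IV.

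**What the model misses.** SAP 5.1, Table 3 gives 5.0% versus 14.2% as detectable with 80% power at n=180 per arm. Use that pair, as an illustration, for the share graded at one visit:

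- Graded subjects: 180 × 0.05 = 9 and 180 × 0.142 = 25.6.
- Exact power of the two-sided 5% Fisher test: 0.814, which agrees with the SAP's 80%.
- Graded-only proportional-odds score test (Wilcoxon with ties), same severity mix in both arms (assumption), 8,000 simulations per mix:

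| Severity mix among graded results | Rejection rate |
|---|---|
| 67/33, Grades 1/2 | 4.6% |
| 80/15/4/1, Grades 1–4 | 4.2% |
| 6/7 Grade 1, 1/7 Grade 2 (the Phase 1 mix) | 4.0% |

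**Direction.** An assumed example shows that the omission can also mislead. Let Normal/G1/G2/G3 be 96/2/1/1% on placebo and 82/16/1/1% on vaccine.

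- Normal kept: odds ratio for being normal = (0.82/0.18) ÷ (0.96/0.04) = 4.56 ÷ 24 = 0.19, worse on vaccine.
- Graded results only: odds ratio for Grade 1 rather than higher = (0.16/0.02) ÷ (0.02/0.02) = 8.0, apparently milder on vaccine.

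**Occupancy of the shift table.** The documents do not give the share graded at baseline; take 2% to 10% as an assumption.

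- No baseline level: 180 × 0.98 = 176 down to 180 × 0.90 = 162 subjects per arm.
- Vaccinees graded on both margins, if grading at the two visits is independent: 180 × 0.02 × 0.142 = 0.5 to 180 × 0.10 × 0.142 = 2.6, spread over 16 cells.
- With full overlap: 180 × 0.02 = 3.6 to 180 × 0.10 = 18.

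Eligibility points the same way for two parameters. ALT at most 1.25 × ULN and platelets at least 125,000 allow at most Grade 1 at screening (Grade 1 is 1.1–2.5 × ULN and 125,000–140,000), although a Day 0 redraw could differ.

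**Estimability.** All four related ALT AEs in Phase 1 were mild. If every graded ALT value here is Grade 1, the outcome has one observed category and the model cannot be fitted.

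**The case against.** The strongest reply is that little depends on this analysis. The SAP makes it optional, says the study is not powered for group differences in these data, and tests no formal hypothesis. New abnormalities appear elsewhere. Table 14.3.4.1, "Distribution of Laboratory Results by Parameter, Severity, Study Day, and Treatment Group", shows Normal, Outside Normal Range and Grades 1 to 4 by arm and visit, with maximum post-baseline severity. Table 14.3.4.2 gives changes from baseline, and Table 14.3.4.3 lists abnormal results. Boxplots and full listings are planned, and abnormalities recorded as AEs enter the Fisher comparison in Table 14.3.1.6. All of that stands and limits the weight of the point. But Table 14.3.4.1 gives counts at each visit, not within-subject shifts, and the protocol commits to the GEE.

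Three further objections stand in part:

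- The simulation gives both arms the same severity mix, so a rejection rate near 5% is built in, and it covers one visit, not repeated measures. It illustrates the logic and is not independent evidence.
- The numeric eligibility limits cover ALT and platelets only. Hemoglobin and WBC may be out of range with physician approval, and the other three affected parameters have no count limit.
- Restriction to graded visits is an inference. One could read the three categories as Normal, Grade 1, and Grade 2 or higher, but nothing says so, and item 2a and the shell say otherwise.

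**Conclusion.** The concern holds. As written, the ordinal shift table has no place for a normal-to-graded change. The ordinal GEE can use graded visits only, and its three categories and two intercepts do not match the four declared grades. These are errors in the specification of seven of the 12 parameters, and they follow from the text without any assumed rates. The power, direction and occupancy figures show scale and rest on the stated assumptions: the Table 3 pair as a per-visit share, the assumed severity mixes, and 2–10% graded at baseline.

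The damage is limited to the baseline-to-follow-up shift and its longitudinal model. The wider laboratory safety comparison survives in the other outputs. The point should be fixed before analysis, but it does not threaten the trial's main safety reporting.

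**What to change.** - In SAP 8.6 item 2a and on both margins of Table 14.3.4.5.x, add Normal/ungraded as the first level, plus a missing category. Define the first level to include values out of range but below Grade 1, and footnote how it relates to the separate Normal and Outside Normal Range rows of Table 14.3.4.1.
- Make item 2b match. Either state a collapse to Normal/ungraded, Grade 1, and Grade 2 or higher, which fits the existing three-category, two-intercept model, or use five categories with four intercepts.
- Name a binary GEE in the form of item 1b, with outcome Grade 1 or above versus ungraded, as the fallback when Grade 2 or higher is too sparse. State that this split differs from item 1's normal/abnormal split.
- Bring the optional wording of SAP 8.6 into line with protocol 6.4.2, or record the change as a deviation from the protocol.

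The cost is SAP and table-shell wording. No new data are needed.
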